A “Go” decision requires: 1) confirmation of target engagement (APS learning, AMPH>PBO,  $p < 0.05$ ); 2) evidence of gains from PACT ( $d \geq 0.5$  (AMPH > PBO)) in primary clinical, neurocognitive and/or functional measures (Fig. 8), and 3) the absence of adverse effects of AMPH that are significantly greater than PBO levels. The decision to not use traditional statistical significance as “Go” criteria for Aim 2 reflects this RFA’s call for “Pilot” studies, the need to identify candidate treatments for a subsequent larger “n” Confirmatory Efficacy R01 study, and the limits in sample size resulting from the 3-year R33 duration. Cohen defined a medium effect size ( $d=0.5$ ) as one that is “visible to the naked eye,” and this amount of change is viewed as clinically meaningful in trials targeting negative symptoms. This  $d=0.5$  “Go” threshold for Aim 2 corresponds to a “number needed to treat” (NNT) value  $\approx 3.62$ . While a “Go” decision does not require identification of a biomarker predicting greater PACT

sensitivity (Aim 3), the identification of one or more meaningful predictors that could be incorporated into a Confirmatory Efficacy trial would favorably impact a “Go” decision.

Staff assessing outcome measures are blind to treatment arm, and for some measures receive training using videotaped and practice interviews until achieving high (ICC>.80) reliability based on 20 assessments by 2 raters. We achieve high inter-rater reliability (e.g., ICC>0.85 for PANSS total), and check for rater drift each 90d.

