**Data Analysis:** “Go/No Go” decisions are based on traditional statistical significance (Aim 1) and effect sizes (Aim 2). Formal statistical testing is conducted using linear mixed-effects (LME) models; hypothesis tests are 2-sided ( $\alpha=0.05$ ). Model parameters are estimated via the R lme4 package and Cohen’s  $d$  is estimated via the EMAtools package. Type I errors are minimized by constraining the number of primary analyses; secondary analyses use false discovery rate corrections. Expected attrition rates are described above. Because outcome measures involve a “change from baseline”, baseline metrics are compared between PBO and AMPH arms, and any baseline differences are addressed in the outcome analyses. Differential drop-out rates from PBO vs. AMPH arms are monitored. Data are assumed to be missing at random; full information maximum likelihood estimators are used, and all data/cases are included in analyses. Clinical follow-up is pursued with all patients exiting the study through post-TCT week 12. Cohort differences: For between-subject contrasts (main effect of drug), differences in age, antipsychotic and anticholinergic loads are tested and used as covariates. Sex differences are tested for all measures based on known sex differences in AMPH sensitivity. NIH Data Harmonization: 3 “PhenX Toolkit” (NOT-MH-15-009) measures of function are used; see above and “Resource Sharing Plan”.

**Aim 1 – Confirm target engagement:** The primary dependent measure of target engagement is AMPH-enhanced APS learning. APS learning is defined as the reduction in Sound Sweeps APS threshold (ms) pre- to post-assessment. Target engagement was demonstrated in MH59803, and will be confirmed if APS learning is increased by AMPH either in a within-subject comparison (AMPH group, “Test 2 vs. 1”), or in a between-subject comparison (AMPH group vs. placebo group change “Test 2” vs. “Test 1”) (note that AMPH and PBO groups are matched by Test 1 PBO performance via stratified randomized assignment). Effect sizes and inferential statistics are based on LME models with random intercepts. A statistically significant main effect of drug (PBO vs. AMPH) on APS learning in either within- or between-subject contrasts is a “Go” criteria and confirms target engagement.

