## Recruitment and Retention Plan

We anticipate that over the course of this study we will consent 69 SZ individuals for screening, from whom we will advance 54 individuals to in-laboratory baseline testing and randomization into two arms with n=27 per arm. After study attrition, we conservatively expect that 36 individuals will complete 30 hours of TCT and longitudinal (12 week post-TCT) testing, and that attrition will be roughly balanced to arrive completed samples of n=18 per study arm.

Example of CONSORT Diagram of proposed R33 study

\* Conservative estimate of final n=18/arm for Aim 2 analyses

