1) Two separate but parallel protocols were approved by the UCSD IRB (protocols #191811, #201502) and posted on ClinicalTrials.gov. Due to the low recruitment numbers, the two parallel studies were combined and placebo groups were pooled, to yield a 3-group design 2) subject randomization changed from 1:1 to a 2:1 active : placebo ratio; and 3) adjustments were made to the planned statistical analyses, appropriate to the reduced sample size.

Based on known benefits of TCT in psychosis patients, no “placebo TCT” condition (e.g., video game) was included, for ethical and pragmatic reasons. Since all subjects received TCT, clinical gains over time in all groups might reflect, to some degree, the benefits of TCT. Pharmacologic augmentation by AMPH would only be evident if/when benefits in “TCT+active drug” groups exceeded those in “TCT+PBO” groups.

The primary goal of this study was to assess the clinical, neurocognitive and functional gains associated with the addition of AMPH to a full course of TCT. In total, there were 3 primary outcome measures and 5 secondary outcome measures. The primary clinical outcome measure was the Positive and Negative Symptom Scale (PANSS) total score; positive and negative subscale scores were secondary outcomes. Because they were highly correlated with total scores ($r=0.92$ at T_1), PANSS general scores are reported but are not outcomes. The primary neurocognitive outcome was the MCCB Composite Score. The primary functional outcome was the World Health Organization Disability Assessment Schedule (WHODAS 2.0, 12-item). Secondary clinical outcome measures also included the Patient Health Questionnaire (PHQ-9), the Young Mania Rating Scale (YMRS) and the Psychotic Symptoms Rating Scale (PSYRATS) hallucinations subscale.

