Clinical, neurocognitive and functional outcome scores were treated as continuous variables and analyzed in three ways. First, they were submitted to linear mixed-effects (LME) models⁵⁹ for both between-group (interaction model: TCT+AMPH vs. TCT+PBO) and within-group (time model: baseline vs. P30, all groups) analyses. LME analyses included data from all randomized subjects (including those who did not complete 30 AT sessions) and modeled random intercepts to account for within-subject dependencies. Second, because sample sizes fell well below target levels, to test the hypothesis that active drugs would augment the impact of a 30-session course of TCT, the effect size (Cohen's d) of the change from baseline to P30 (“difference score”) was calculated for both between-group (TCT+AMPH vs. AT+PBO) and within-group (baseline vs. P30, all groups) comparisons. Between-group effect sizes were calculated as:

$$d = [(drug score T_1 - drug score P30) - (PBO score T_1 - PBO score P30)] / SD_{wav}$$

where SD_{wav} is the weighted average standard deviation. Within-group effect sizes were calculated as:

$$d = (score at T_1 - score at P30) / SD_{av}$$

where SD_{av} is the average of the standard deviations of the T_1 and P30 measures^{60,61}.

Third, to disentangle the salutary contributions of TCT alone vs. TCT+active drug to within-subject effect sizes, a “threshold” for positive active drug effects was set at “*d=0.4 above PBO values*”:

$$d(\text{active drug}) \geq d(\text{PBO}) + 0.4.$$

Because clinical gains from TCT+PBO were expected to be approximately $d=0.4$, this added threshold of “ $d=0.4$ above PBO” for drug-enhanced TCT meant that an estimated combined large effect size (at least $d=0.8$) would be required for a drug effect to be viewed as meaningful. Outcomes using thresholds from $d=0.2$ to $d=0.6$ were reported.

The use of effect size comparisons in addition to p-values is common in clinical trials research as a way to measure effects independent of sample size. It is particularly useful when, as in the current study, sample sizes fall below targets identified based on traditional power analyses. Effect size “thresholds” have been used by others to argue that TCT neurocognitive benefits exceed levels produced via PBO or practice effects (generally $d \approx 0.18$).

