Indirect indicators of clinical impact included subject attrition, C-SSRS responses, treatment satisfaction and adverse events (AEs). AMPH group subjects were evaluated for abnormal involuntary movements (AIMS) and for deleterious effects of AMPH cessation (AMPH Cessation Symptom Assessment). Analyses included non-parametric (Chi-Square) and parametric (rmANOVA) tests.

Linear mixed-effects models for outcome measures included all subjects who were randomized; df were estimated using the Satterthwaite approximation. Between- and within-group effect sizes for clinical, neurocognitive and functional measures were calculated based on all subjects who completed 30 TCT visits and P30 testing (“completers”). For all analyses, α was set at 0.05; for analyses of the 5 secondary outcome measures, findings were also evaluated with a more restrictive alpha level (0.01) to correct for multiple comparisons.

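### The safety condition for Go is met by a non-significant difference in adverse effects, which at this sample size often would not reveal a moderate real excess

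*Protocol*

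**What the plan says.** The paragraph on Outcome and Go Decisions in the protocol sets three requirements for Go: target engagement at p<0.05, an effect of at least d=0.5 on a primary outcome, and "the absence of adverse effects of AMPH that are significantly greater than PBO levels". The third stands only in the text. The Fig. 8 box and the Go/No-Go section of the SAP do not list it.

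No measure, margin, confidence limit or power is attached to it. The test level has to be taken from the general statements. The protocol's Data Analysis section says that "hypothesis tests are 2-sided" at 0.05. The SAP's Project Modification says "For all analyses, α was set at 0.05" and, for a group of indicators that includes adverse events, "Analyses included non-parametric (Chi-Square) and parametric (rmANOVA) tests".

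The planned size is "randomization into two arms with n=27 per arm". The modification later reports that "subject randomization changed from 1:1 to a 2:1 active : placebo ratio" and explains its use of effect sizes "because sample sizes fell well below target levels". It neither restates nor replaces the safety condition.

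**The concern.** A non-significant test shows only that the data did not exclude equality. It does not show that an excess is absent, and in a small trial the two are far apart. The protocol recognises this for benefit. Under Limitation #6 it says that the sample will not easily reach p<0.05 between groups, and under Outcome and Go Decisions it cites limited sample size as a reason for judging Aim 2 by effect size. For harm it keeps the significance test, and there a non-significant result favours Go. Low power is relieved where it would block Go and left in place where it helps.

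At stake is what a Go decision would say. It would carry amphetamine into a larger trial in psychosis with the safety condition recorded as met, although the comparison may have had little chance of failing.

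**Working it through.** **The plan's own figure.** The only power calculation is for target engagement: d=0.5, 80% power, two-sided 0.05, test-retest correlation 0.8, 27 per group. Taken as a comparison of change scores, the SD of change is √(2×(1−0.8)) = 0.632. The non-centrality at n=27 is (0.5/0.632)×√(27/2) = 2.91, which gives 81.3% power; n=26 gives 79.8%. So 27 is reproduced. It says nothing about adverse events.

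**Inputs for the safety condition.** There are 27 randomised per arm (Recruitment and Retention Plan) and the test is two-sided at 0.05. The SAP names chi-square; Fisher's exact test is added because expected counts are small. *Assumption:* the documents give no expected AE rate for either arm, so placebo is taken as 5% or 10% and the amphetamine rate is varied.

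**Formula.** The chance that the condition fails, as it should when there is a real excess, is

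Σₐ Σ_b Bin(a; n_A, p_A) × Bin(b; n_P, p_P), summed over all (a, b) with p<0.05 and a/n_A > b/n_P.

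| Placebo | Amphetamine | Excess (points) | Fisher | Chi-square |
|---|---|---|---|---|
| 5% | 15% | 10 | 7% | 23% |
| 10% | 20% | 10 | 8% | 19% |
| 5% | 20% | 15 | 19% | 41% |
| 5% | 25% | 20 | 36% | 60% |
| 10% | 30% | 20 | 31% | 49% |
| 10% | 40% | 30 | 63% | 77% |
| 10% | 50% | 40 | 87% | 93% |

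**What one passing result could look like.** Take 8/27 on amphetamine and 3/27 on placebo. The difference is 29.6% − 11.1% = 18.5 points, with a Newcombe 95% interval of about −3 to +39. Chi-square = 54×(8×24 − 3×19)²/(27×27×11×43) = 2.85, p=0.09; Fisher p=0.18. The condition is met although the interval includes an excess of nearly 40 points. With equal counts of 3/27 the interval is about ±18 points.

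**After the modification.** The final numbers are not given. Two illustrations for 30% versus 10%: 36 amphetamine and 18 placebo (the planned 54 split 2:1) gives 32-36%; 20 and 10 gives 10-16%. The loss comes mainly from the smaller total; at 54 patients the split lowers the chi-square figure but hardly moves the Fisher one. Because placebo groups were pooled across two protocols, the ratio in the amphetamine comparison need not be 2:1.

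**If the comparison is a score.** For a change score with r=0.8, power for d=0.5 at 27 per arm is the 81% above. For a final score alone it is 44%. The 0.8 is borrowed from the auditory-learning calculation and is not documented for any safety scale.

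**The case against.** The strongest objection is that the rule does not speak of incidence. It refers to placebo levels, which could mean scale scores; the protocol says that adverse effects on psychosis, akathisia and other symptoms will be assessed by clinical metrics, and the SAP includes repeated-measures ANOVA. On that reading power may be adequate for a medium effect. This stands as a limit on the figures: the low power is shown for event proportions. It does not rescue the rule, because a non-significant score difference is still not evidence of no harm, and the measure is left undefined.

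Second, a reader might infer that the condition is passed most of the time whenever amphetamine multiplies the rate several-fold. The table does not support that. A fivefold increase from 5% to 25% is flagged 60% of the time by chi-square, and 40% or 50% against 10% is usually caught.

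Third, it is tempting to quote still lower power at 18 per arm. That is the number expected to complete training: "attrition will be roughly balanced to arrive completed samples of n=18 per study arm". Adverse events are recorded from consent until after last participation, so 27 randomised per arm is the planned base.

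Fourth, safety does not rest on this test alone. The Data and Safety Monitoring plan provides quarterly review, a three-SAE rule and a review of final results, and Study Halting adds a rule on grade 3 events. These matter for participants during the trial. They do not define the Go condition or change what a non-significant p-value means.

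Finally, one might say that poor recruitment makes Go easier. That holds only for the safety condition taken alone; target engagement at p<0.05 becomes harder to reach as numbers fall.

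**Conclusion.** The concern holds for moderate excesses in event incidence. At 27 per arm, with placebo rates assumed at 5-10%, a 10- to 15-point excess would be flagged in 7-41% of trials and a 20-point excess in 31-60%, depending on the placebo rate and the test. An excess of 30 points or more over 10% would usually be detected (63-93%). Enrolment below target lowers these figures, by an amount the documents do not let one fix.

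The documents do not support the stronger inferences that the trial is without safety protection or that no excess could be found. The defect is in the decision rule: followed as written, it records a failure to detect harm as absence of harm, in a plan that has already accepted this limitation for efficacy. All power figures rest on assumed event rates. The meaning of a non-significant result does not.

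**What to change.** In the protocol's Outcome and Go Decisions paragraph, and in the SAP's Go/No-Go section, replace the non-significance condition with estimation:

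- Report the amphetamine minus placebo difference with a 95% confidence interval, in all randomised patients who received study drug, for the incidence of any AE, of SAEs and of symptom worsening. Do the same for the safety scales already collected.
- State in the SAP how each of these is counted.
- Base the safety part of Go on the estimate and its upper confidence limit, considered with the monitoring board at the final review that the protocol already provides.
- Do not describe a non-significant result as absence of adverse effects.

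No extra patients, visits or measurements are needed, and no clinical rule changes. If enrolment is over, the change can still be made at reporting, and it matches the effect-size approach that the SAP modification takes for efficacy. The cost is that the safety statement becomes less reassuring: even equal counts of 3/27 leave an interval of about ±18 points. The upper limit then informs a judgement and is not a pass mark. A formal margin would be demanding: with 10% in both arms, ruling out a 15-point excess (one-sided 0.025, 80% power) would take 63 per arm and a 20-point excess 36 per arm. Both margins are illustrations only.

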A prerequisite for AMPH’s utility in a PACT application is that it have appreciable pro-cognitive effects in patients. As noted above, the literature provides evidence that a single small oral dose of AMPH can modestly enhance neurocognition in SZ- and SZ-spectrum patients, without adverse effects, and our findings confirmed this with 5 and 10 mg doses. However, there are limitations to this literature. First, the magnitude of pro-cognitive effects of AMPH in most studies is modest. AMPH-induced gains in non-motor measures in Goldberg et al. reached “trend” levels; in Barch & Carter, they reflected planned contrasts and the loss of trend-level deficits in patients vs. HS; in Petrzak et al. they were robust in one report with 10 mg po, but moderate in another with 20 mg po ( $d = 0.63$ ). Second, meaningful comparisons across these studies, and with subsequent studies of other putative pro-cognitive agents, are confounded by a lack of shared performance measures. Until recently, no studies had tested the effects of AMPH on neurocognition in SZ patients using the MCCB, considered the “gold standard” for repeatable measures of pro-cognitive drug effects in SZ; nor had any studies in SZ patients assessed the utility of biomarkers to identify patients most likely to exhibit AMPH sensitivity, as discussed below. And of greatest relevance to this application, until the PI’s studies supported by MH59803, no study had tested the effects of AMPH on learning processes specifically engaged by cognitive training in SZ patients.

**2. Preliminary studies**: AMPH effects on Sound sweeps learning. A. Subjects identify “sweep direction” of frequency modulated tones; adaptive trials increase in utility as subject learns. B. Auditory Processing Speed (APS, in ms; smaller # = better discrimination) is calculated pre- and post-training. APS “learning” is defined as “APS pre minus APS post”. C. At screening, healthy subjects tend to “learn” more than SZ patients. D. In a within-subject design, 10 mg AMPH enhanced APS learning in both healthy and SZ patients. E. AMPH-induced gains in APS learning “held forward” to pre-testing 1 wk later; this did not happen if no pill or PBO was received the previous week.

[figure not shown]

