#### **Preliminary Studies:** 1. Amphetamine effects on auditory frequency modulation learning in SZ patients.

MH59803 tested the hypothesis that AMPH will enhance learning of auditory frequency modulation in “Sound Sweeps” -- a major component of the Posit Science TCT program known to enhance clinical, neurocognitive and functional status in SZ patients. We reported that performance in this Sound Sweeps task is dependent on attention, and we hypothesized that gains in the main performance metric of auditory processing speed (APS) would be augmented by the pro-attention drug, AMPH. APS was measured in 24 AP-medicated SZ patients and 35 healthy subjects on 3 days, each separated by 1 week. Specific candidate biomarkers were assessed as potential predictors of sensitivity to AMPH-enhanced gains in APS among patients, including prepulse inhibition (PPI) of startle, specific event-related potentials (ERPs), neurocognition (MCCB) and the rs4680 polymorphism of catechol-O-methyltransferase. On two test days, subjects ingested either PBO or 10 mg AMPH po, in a double-blind, balanced order design; TCT, PPI and MCCB measures were repeated on each test day.

Auditory system “learning” (APS pre- vs. post-training) 210 min post-pill was significantly **enhanced by 10 mg AMPH (p<0.002), particularly in SZ patients** (Fig. 2D); rs4680 status did not moderate AMPH effects on APS. Among patients, more APS learning was associated with **AMPH-induced increases in attention** (MCCB “A/V” domain:  $r=0.34$ ,  $p<0.05$ ) and **shorter latency of the P3a ERP** ( $r=-0.43$ ,  $p<0.035$ ). There were no significant “order effects”: AMPH enhanced APS learning whether it preceded or followed placebo testing. AMPH-enhanced learning was **not state-dependent**: it “carried forward” to the next testing day, 1 week later (Fig. 2E). There were no adverse effects of AMPH, consistent with our experience with higher doses of AMPH (20 mg po) in HS. Subjectively, participants could not guess pill identity at greater than chance levels, while objective / blind measures of alertness, hedonia and autonomic function confirmed AMPH bioactivity.

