**Specific Procedures: TCT** is completed with a dedicated room and equipment. Staff trained with a UCSD-developed “TCT Clinician Competence Assessment” monitor TCT, clarify instructions and provide encouragement as needed. In the initial “biomarker testing” session (Test 1), all subjects receive a PBO pill and complete 1-h of Sound Sweeps to generate a “PBO APS score” as described previously (Fig. 2A,B). Treatment group assignment (PBO vs. AMPH) is then made using stratified random sampling (above), and 5-7 days later patients ingest either PBO (n=27) or 5 mg AMPH (n=27) 60 min before completing the Sound Sweeps session (“Test 2”). AMPH effects on APS learning are assessed both within-subject (APS (Test 1 - Test 2) for AMPH group subjects: a key measure of AMPH sensitivity) and between subjects (APS Test 2, PBO vs. AMPH groups). For all other sessions, subjects receive either PBO or AMPH 60 min before TCT, which includes 5 modules of auditory/verbal processing exercises. Each module increases in difficulty as performance improves: 1) Sound Sweeps; 2) Syllable Identification: Patients distinguish between 2 similar phonemes (e.g., “ba” vs. “da”), differing only in their voice onset time; 3) Word Matching: Subjects match short similar-sounding consonant-vowel-consonant words (e.g., bad, dad); 4) Listen & Do: Subjects reconstruct a spoken series of instructions and use a computer mouse to click icons on the screen in a specified order. This exercise is designed to stimulate verbal WM processes supported by the lateral PFC as well as premotor and motor processes. 5) Rhythm Recall: Subjects listen to and replicate a short rhythmic sequence. This task is designed to stimulate both basic auditory processes supported by primary auditory cortex, and non-verbal auditory WM.

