### 4.3. Outcome Measures

Type	Name	Time Frame	Brief Description
Primary	Auditory Processing Speed (APS) learning	Test 1 and Test 2, one week apart	APS is measured before and after the TCT "Sound Sweeps" frequency modulation session, to determine the amount of "learning", based on the reduction in detection gap (ms). More learning (greater gain in processing speed) with amphetamine vs. placebo confirms target engagement, which is the primary outcome of Aim 1.
Primary	PANSS: Positive & Negative Symptom Scale total	baseline vs. post-TCT session 10, 20 and 30 (approximately 10 weeks), and 12 weeks post-TCT	TCT reduces both positive and negative symptoms of psychosis; we predict that amphetamine will augment these effects via enhanced TCT learning, detected by the PANSS. For this reason, and based on the need to limit total outcome measures, PANSS Total Score is the primary clinical outcome measure. Positive and negative symptom subscales, as well as PANSS factor-derived measures, will be assessed in exploratory analyses. Other secondary clinical measures will include: 1) Psychotic Symptom Rating Scales (assesses auditory hallucinations); 2) Young Mania Rating Scale; 3) Patient Health Questionnaire-9 (current depressive symptoms); 4) Abnormal Involuntary Movement Scale; 5) Columbia Suicide Severity Rating (C-SSRS); "Lifetime/Recent version" at screen; "Since Last Visit" at follow-up visits). The C-SSRS is a sensitive measure of suicidal ideation; any "yes" in C-SSRS prompts an immediate full evaluation/action plan by a study M.D.; and 7) AMPH Cessation Symptom Assessment

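### Aim 1 target engagement can be confirmed by an uncontrolled Test 1 to Test 2 change within the AMPH arm, without any difference from placebo

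*Protocol*

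**What the plan says.** The Protocol's Data Analysis section, under Aim 1, gives the rule twice. Target engagement "will be confirmed if APS learning is increased by AMPH either in a within-subject comparison" (AMPH group, Test 2 against Test 1) or in a between-subject comparison of change. It then adds that a significant main effect of drug "on APS learning in either within- or between-subject contrasts is a" Go criterion.

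Under Specific Procedures: TCT, at Test 1 "all subjects receive a PBO pill and complete 1-h of Sound Sweeps". Randomisation follows, and Test 2 takes place 5-7 days later on the assigned pill. The same section defines the controlled contrast as "between subjects (APS Test 2, PBO vs. AMPH groups"), that is, on Test 2 alone, whereas Aim 1 defines it on the change from Test 1 to Test 2.

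Other sections word the criterion as drug against placebo. Outcome and Go Decisions requires "confirmation of target engagement (APS learning, AMPH>PBO" at p<0.05), and Fig. 8 agrees. Section 4.3 states: "More learning (greater gain in processing speed) with amphetamine vs. placebo confirms target engagement". The SAP's Primary Efficacy Endpoint(s) paragraph refers to AMPH versus PBO conditions without naming a contrast. None of these withdraws the within-arm route, and the SAP's Project Modification does not restate the Aim 1 test.

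**The concern.** In the AMPH arm the order is always placebo first and AMPH second. A change between the two tests may come from the drug, from having done Sound Sweeps before, or from time. A concurrent placebo arm takes the same two tests and could separate these, but the within-arm route ignores it. If both arms improved equally, the criterion could still be met.

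Target engagement is a mandatory Go condition and the only one the trial is powered to test for significance. It is also listed as a primary outcome in section 4.3. The Protocol's discussion of negative results interprets a null Aim 2 according to whether engagement was shown, so a false confirmation would also distort that reading: the conclusion would be that enhanced learning is not sufficient, when enhanced learning had not been shown.

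The two definitions of the between-arm contrast add to the problem, because the primary Aim 1 analysis is not uniquely specified.

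**Working it through.** **Inputs from the documents.** d = 0.5, 80% power, two-sided alpha 0.05, test-retest correlation r = 0.8, 27 per group (Power analyses, Protocol and SAP). Placebo for all at Test 1; Test 2 about 5-7 days later.

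**Input assumed.** A Test 1 to Test 2 shift k in APS learning, common to both arms, in SD units. The documents give no value, so a range is shown.

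**Step 1: which contrast does 27 per group belong to?** The SD of the change is √(2(1 − 0.8)) = 0.632, so d = 0.5 becomes 0.5/0.632 = 0.79 on the change scale.

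| Contrast | Power at d = 0.5 |
|---|---|
| Between arms, change, two-sample t | 79.8% at 26 per arm; 81.3% at 27 |
| Between arms, Test 2 adjusted for Test 1, residual SD √(1 − 0.8²) = 0.6 | 85.2% at 27 per arm |
| Between arms, Test 2 only, SD 1 | 43.8% at 27 per arm |
| Within AMPH arm, paired t, no shift | 81.2% at n = 15; 97.7% at n = 27 |

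The plan's figure is reproduced by the between-arm contrast of change: 27 is the first n to reach 80%. The trial was sized for the controlled comparison. The within-arm test would have needed about 15.

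**Step 2: how small a shift passes the within-arm test?** The standard error is 0.632/√27 = 0.122 and the critical t on 26 df is 2.056. An observed mean change of 0.122 × 2.056 = 0.25 SD in the AMPH arm gives p<0.05, whatever the placebo arm shows.

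**Step 3: false confirmation with no drug effect.** The within-arm noncentrality is k/0.122, or 0.82, 1.64 and 2.46 for k = 0.1, 0.2 and 0.3. The either/or rates come from simulation (100,000 to 400,000 trials per setting) with 27 per arm, a paired t-test in the AMPH arm or a two-sample t-test on change, counting only results that favour AMPH.

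| Assumed shift k | Either/or, r = 0.8 | Between-arm only | Either/or, r = 0.5 |
|---|---|---|---|
| −0.2 SD | 2.5% | 2.5% | not run |
| −0.1 SD | 2.7% | 2.5% | not run |
| 0 | 4.2% | 2.5% | 4.2% |
| +0.1 SD | 13% | 2.5% | 8% |
| +0.2 SD | 35% | 2.5% | 17% |
| +0.3 SD | 66% | 2.5% | 32% |

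A noncentral-t check of the within-arm test alone at r = 0.8 gives 12%, 35% and 66% at k = 0.1, 0.2 and 0.3. At k = +0.2 and r = 0.8, (35.5 − 2.5)/35.5 = 93% of confirmations come from the within-arm test alone. Counting both directions at zero shift, the rule's error is 8.3% against a nominal 5%.

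**Step 4: an unfavourable shift.** With a true d = 0.5 and k = −0.2, the net within-arm change is 0.3 SD. Within-arm power falls from 98% to 66%, while between-arm power stays at 81%. The within-arm contrast is unreliable in either direction.

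**The case against.** The large error rates need a favourable retest shift, and the documents lean against one. The outcome is the gain within a session, so prior exposure could lower it as easily as raise it. On whether gains carried forward to the next pre-test, the preliminary data report that "this did not happen if no pill or PBO was received the previous week". In a balanced-order 10 mg study of 24 patients and 35 healthy subjects, "AMPH enhanced APS learning whether it preceded or followed placebo testing", with no significant order effects. Without any shift, the inflation is only from 2.5% to 4.2%. The steeper series also depends on r = 0.8; at r = 0.5 the rate at +0.2 SD is halved.

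The consequence is bounded too. A Go still requires a between-arm d of at least 0.5 on an Aim 2 measure and no significant excess of adverse effects. Most statements of the criterion already read as AMPH against placebo. The SAP's Project Modification names three primary outcomes (PANSS total, MCCB composite, WHODAS) and APS learning is not among them, so the current standing of Aim 1 is unclear.

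These points limit the size and reach of the problem; they do not remove it. A non-significant order effect in a study of that size does not exclude a shift of 0.2-0.3 SD, and this trial has no balanced order within the AMPH arm. Nothing in either document withdraws the either/or rule, and the SAP still carries Aim 1 as a primary endpoint. The difference between the two between-arm definitions is a matter of power (44% against 81%), not of bias, and is secondary.

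**Conclusion.** The concern holds. As written, Aim 1 can be declared confirmed on an uncontrolled pre-post change even when AMPH and placebo do not differ. With no retest shift, the favourable-direction error is 4.2% instead of 2.5%. With an assumed common shift of +0.1 to +0.3 SD it is 13% to 66% at r = 0.8, and 8% to 32% at r = 0.5. Since the sign and size of the shift are assumptions, these figures show how exposed the rule is; they are not an expected error rate. The harm is confined to the target-engagement result and what is inferred from it, because the overall Go cannot be reached by this route alone. It should be fixed.

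**What to change.** Make one between-arm contrast the sole Aim 1 test: the arm effect on Test 2 APS learning adjusted for Test 1 APS learning (or the arm-by-test interaction), two-sided at 0.05. Remove the within-subject alternative from both sentences under Aim 1, align the Test 2-only definition under Specific Procedures: TCT, and state the same test in the SAP, including whether Aim 1 remains a primary endpoint after the Project Modification.

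Report the Test 1 to Test 2 change with confidence intervals in both arms; the placebo arm then shows the retest shift directly. The within-subject change can keep its role as a measure of AMPH sensitivity and as a predictor in the secondary Aim 2 regressions. It should only stop being a confirmation criterion.

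For the original 1:1 design this costs wording only: 27 per arm gives 81% power on change and 85% with Test 1 as covariate. What is given up is an easier route to confirmation (98% power within the arm if there is no shift). Under the later three-group design with 2:1 randomisation and pooled placebo, power cannot be stated because the documents give no arm sizes; it should be recalculated from the actual numbers.
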